- Bone scans and CT/MRI of the chest, abdomen, and pelvis will be done every 3 months (window for tumor assessment is ±7 days of respective visit day). PCWG3 and iRECIST guidelines for imaging will apply. See Section 8.1.1.1.
- [7] On-treatment tumor samples from biopsies or tumor resections done as part of the clinical management of the patient (e.g., palliative surgery) will optionally be provided for additional potential biomarker research.

CONFIDENTIAL Page 34 of 122

- [8] For details on safety laboratory tests, see Section 10.2. If warranted by dipstick results, urine sediment will be microscopically examined.
- [9] Thyroid hormones (thyroid stimulating hormone [TSH], free thyroxine [fT4] and triiodothyronine [T3]) will be performed every 6 weeks, at Safety FU D90, or as clinically indicated at the investigator's discretion.
- [10] At treatment visits, patients will also be monitored for TEAEs at site, according to local prescribing guidelines for cemiplimab.
- [11] For details on patient's survival status and disease status, see Sections 8.1 and 10.9.
- [12] Sampling at CemC3 or at EoT, whichever occurs first.
- [13] Only if routinely performed locally.
- [14] Assessments will be performed at CemC1, CemC4, CemC7 and when considered as clinically indicated by the investigator.

CONFIDENTIAL Page 35 of 122

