## 10.9. Appendix 9: Criteria for Disease Response Assessment

#### 1. MEASURES OF PROGRESSION AFTER COMMENCMENT OF TREATMENT:

Progression will be documented by confirmed radiograph progression (bone and/or CT/MRI scan with a subsequent confirmatory scan) and/or unequivocal clinical progression. Patients should **not discontinue treatment on the basis of PSA progression alone** and instead this should guide the investigator to potentially expedite radiological investigations.

The criteria for disease progression are considered met if one or more of the following conditions occur:

- a) Radiological progression per PCWG3:
  - Soft tissue/visceral disease progression:
    - A patient will be determined to have progressed if they have progression of target lesions (sum of diameter increase to nadir of ≥20% and by ≥5 mm), clear progression of existing non-target lesions, or the appearance of 1 or more new lesions. Lymph nodes have to be ≥ 1.5 cm in short axis to be deemed measurable.
    - The scan for confirmation of progression may be performed ≥4 and ≤8 weeks after the initial scan demonstrating progression. Patients who have a repeat scan earlier than scheduled and do not confirm progression do not need to undergo the next scheduled imaging if it is <4 weeks after the confirmation scan. Patients will return to their regular imaging schedule starting with the next time point.

  - Bone disease progression
    - On the C3D15 scan, ≥2 new lesions compared with baseline confirmed by a second scan ≥6 weeks later that also shows an additional ≥2 new bone lesions (2+2 rule, i.e., a total of ≥4 new lesions compared with the baseline bone scan).
    - On subsequent scans (>16 weeks), ≥2 new bone lesions compared with the previous scan with the confirmatory scan at ≥6 weeks demonstrating at least persistence of the progression noted on the previous scan.
- b) Unequivocal evidence of clinical progression
- c) PSA Progression

CONFIDENTIAL Page 113 of 122

- ≥25% increase and an absolute ≥2 ng/mL rise This rise must be confirmed by a second measurement ≥3 weeks later and the date of progression is denoted as the first measurement to meet these criteria. Ignore early rises (before 12 weeks) in determining PSA progression.
- If the PSA has risen during the first 12 weeks and then decreased, the ≥25% increase and an absolute ≥2 ng/mL rise is required above the new decreased value (nadir value), confirmed by a second measurement at least 3 weeks later.

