8.2 Key definitions

Date/time of first administration of IMP (W_pro1 or Cemiplimab):

Is defined as first administration date/time of IMP (W_pro1 or cemiplimab), whichever was administered first.

Baseline Definition:

Baseline is defined as last available value prior to or on the date/time of first administration of IMP (W_pro1 or cemiplimab, whichever was administered first). Unscheduled measurements prior to first administration of IMP will be considered in the calculation of the baseline values. In the case that date/time of first administration of IMP is missing (i.e.,

for randomized not treated patients) the date/time of randomization will be used for the definition of baseline values.

Cemiplimab Baseline – Baseline definition for Arm 1B patients who switch to cemiplimab monotherapy:

Cemiplimab Baseline is defined as last available value prior to or on the date/time of first administration of cemiplimab.

In case no time of the assessment is reported, measurements at the same date as first administration of cemiplimab will be considered as baseline.

Change and percent change from baseline:

Change from baseline will be calculated as follows:

- Change from baseline = post-baseline assessment value – baseline assessment value.
- Percent change from baseline = (post-baseline assessment value – baseline assessment value) / baseline assessment value * 100.

Age (in years) at date of informed consent:

Age is derived in the database based on the collected Year of birth as follows:

Age = ICF Date – (01July + Year of birth) / 365.25.

Age as derived in the database will be used for all analyses.

Body mass index (BMI):

BMI will be calculated as follows:

$$\text{BMI} \left(\frac{\text{kg}}{\text{m}^2} \right) = \frac{\text{Weight (kg)}}{\text{Height(m)}^2}$$

Duration:

Duration will be calculated as follows:

- Duration (days) = last observation date – first observation date + 1

For conversion of days to months or years the following rules will be applied:

- 1 month = 30.4375 days
- 1 year = 365.25 days

Time from first diagnosis to enrollment (in months):

Date of initial diagnosis is collected in Month/Year. Missing day will be replaced with the first day of the month. In case month is not reported, missing month will be replaced with July.

Time from first diagnosis to enrollment (months) will be calculated as:

(ICF date – imputed date of initial diagnosis) / 30.4375

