The BOR is defined as a single best response status at any tumor response assessment after first administration of IMP and prior to or at the start date of the first subsequent anti-cancer therapy. Overall response of PD within 14 days after the start date of the first subsequent anti-cancer therapy will be considered.

Only responses up to and including the date of the first progressive disease will be considered in the derivation of the BOR.

The following order of tumor response categories will be used, with “Complete Response” is the best category:

Complete Response (CR) – Partial Response (PR) – Stable Disease (SD) – Progressive Disease (PD) – Not Evaluable (NE) – Not Applicable (NA).

Best Overall Response (BOR) based on iRECIST (central reading):

The following order of tumor response categories will be used to define the BOR category based on iRECIST (central reading), with “Complete Response” is the best category:

Complete Response (iCR) – Partial Response (iPR) – Stable Disease (iSD) - Unconfirmed Progressive Disease (iUPD) – Confirmed Progressive Disease (iCPD) – Not Evaluable (NE) – Not Applicable (NA).

Only central reading assessments after first administration of IMP and prior to or at the start date of the first subsequent anti-cancer therapy will be considered in the derivation. Overall response of iUPD or iCPD within 14 days after the start date of the first subsequent anti-cancer therapy will be considered.

Only responses up to and including the date of the first progressive disease will be considered in the derivation of the BOR.

Further information on the definition of the BOR based on iRECIST is available in Section [13.3](#).

PSA Response definition based on PCWG3:

PSA response definition based on PCWG3 will be derived based on the PSA response data reported by the investigator.

If a PSA PD occurred \geq 12 weeks after first administration of IMP. This PSA PD needs no confirmation.

For the derivation of best overall PSA Response based on PCWG3, the PSA responses have to be **confirmed**. The following rules have to be implemented for PSA response confirmation:

- **PSA PR Response Confirmation**
 - PSA PR needs to be confirmed by:
 - Subsequent [Radiological Soft Tissue PR or CR response] or
 - Subsequent [PSA PR response]

- Which occurs within ≥ 20 days and \leq start date of first subsequent anti-cancer therapy, immediately after initial PSA PR response

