 - With no worse response (SD, PD) between initial PR and confirmation response
 - Worse responses are defined as [Radiological Soft Tissue SD or PD response] or [Clinical Progression Event] or [Progressive Bone Disease] or [PSA SD or PD response]
- **PSA SD Response Confirmation**
 - PSA SD needs to be confirmed by:
 - Subsequent [Radiological Soft Tissue SD, PR or CR response] or Subsequent [PSA SD or PR response]
 - Which occurs within ≥ 20 days and \leq start date of first subsequent anti-cancer therapy, immediately after initial PSA SD response
 - With no worse response (PD) between initial SD and confirmation response
 - Worse responses are defined as [Radiological Soft Tissue PD response] or [Clinical Progression Event] or [Progressive Bone Disease] or [PSA PD response]
 - **PSA PD Response Confirmation**
 - If a PSA PD occurred < 12 weeks after first administration of IMP, this PSA PD needs to be confirmed by:
 - Another PSA PD that occurred immediately after the initial PSA PD and ≥ 12 weeks after first administration of IMP and \leq start date of first subsequent anti-cancer therapy + 14, immediately after the initial PSA PD response.
 - Subsequent [Radiological Soft Tissue PD] or [Clinical Progression] or [Progressive Bone Disease] immediately after the initial PSA PD and \leq start date of first subsequent anti-cancer therapy + 14.
 - PSA PD confirmation can only occur if there are no better responses (CR, PR, SD) between the initial PSA PD and confirmation assessment.
 - Better responses are defined as [Radiological Soft Tissue CR, PR or SD response] or [PSA PR, SD response]

Best Overall PSA Response definition based on PCWG3:

The best overall PSA response based on PCWG3 is defined as a single best PSA **confirmed** response status at any response assessment after first administration of IMP and prior to or at the start date of the first subsequent anti-cancer therapy. Overall response of PD within 14 days after the start of the first subsequent anti-cancer therapy will be considered.

Only responses up to and including the date of the first progressive disease will be considered in the derivation of the best overall PSA Response.

The following order of response categories will be used, with “Partial Response” is the best category:

Partial Response (PR) – Stable Disease (SD) – Progressive Disease (PD) – Unknown – Not Applicable (NA).

Best Overall Response (BOR) based on PCWG3:

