The rules for the definition of BOR based on PCWG3 are referring to the following data reported in the CRF:

- Confirmed PSA response reported by the investigator (see Section 8.2 for more details regarding PSA response confirmation)
- Radiological Soft Tissue Evaluation (response data collected in the CRF on the “RECIST 1.1” page)
- Clinical Progression (data collected in the CRF on the “Clinical Progression” page)
- Bone Disease Progression (data collected in the CRF on the “Bone Lesion” pages with Clinical Impression = Progression)

Only assessments after first administration of IMP and prior to or at the start date of the first subsequent anti-cancer therapy will be considered in the derivation. Overall response of PD within 14 days after start date of the first subsequent anti-cancer therapy will be considered.

Only responses up to and including the date of the first progressive disease will be considered in the derivation of the BOR.

Overall Response of CR, PR, SD per PCWG3 is based on radiological soft tissue response or confirmed PSA response.

Progression of Disease per PCWG3 is based on the earliest radiological soft tissue progression, Bone disease progression, confirmed PSA progression or clinical progression.

The following order of tumor response categories will be used, with “Complete Response” is the best category:

Complete Response (CR) – Partial Response (PR) – Stable Disease (SD) – Progressive Disease (PD) – Not Evaluable (NE) – Not Applicable (NA).

Derivation of PSADT:

PSADT will be derived based on the PSA measurements provided by the investigator in the database and collected during the trial at screening visit and during each cycle.

PSADT will be calculated post-treatment on C4D1 and D1 of every fourth subsequent cycle (e.g. C8D1, C12D1, etc.) in Part 1 and Part 2 Arms 1A and 1B, or on C4D1, C8D1, and EoT in Part 2 Arms 2 and 3.

PSA measurements reported after EoT visit or after start of the first subsequent anti-cancer therapy will not be considered in the derivation of PSADT.

PSADT will be calculated using a linear regression model of the natural logarithm of PSA values and time ([3] and [<https://drhaddad.com.au/wp-content/uploads/2022/07/13.pdf>], [8]).

Derivation of PSADT post-treatment at every fourth subsequent cycle:

1. Compute the slope of the regression line of natural logarithm of PSA vs. time (which is the number of doublings per unit time) where PSA is the PSA level in ng/mL at each time point

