OS is defined as the time from the date of the first dose of IMP to the date of death from any cause. OS will be analyzed using the Kaplan-Meier method. Kaplan-Meier plots will be generated.

In case date of death is reported after trial discontinuation date, this data will not be considered in the OS and the patient will be censored at the day of their last date known to be alive.

Patients alive or patients lost to follow-up at the date of analysis cut-off will be censored at the day of their last date known to be alive.

OS expressed in months = (Date of death from any cause – date of first dose of IMP + 1) / 30.4375 for patients with available death date

or

(Last date of known to be alive – date of first dose of IMP + 1) / 30.4375 in case of censoring.

In the case that date of the first dose of IMP is missing, randomization date will be used for the calculation of OS.

8.7.4.2 Exploratory efficacy endpoints for patients in Arm 1B who are treated with cemiplimab monotherapy following progression on W_pro1

Patients in Arm 1B will be given the option to be treated with cemiplimab monotherapy following progression on W_pro1 monotherapy treatment and will be assessed for some exploratory efficacy endpoints, where the last measurement prior to start of cemiplimab treatment will serve as baseline measurement and the time-to-event endpoints (DoR, and PFS) will start from first dose of cemiplimab treatment. In particular, the last radiographic tumor assessment prior to cemiplimab treatment will re-define target and non-target lesions as basis for tumor response assessment on cemiplimab treatment. Additionally, PFS2 will be evaluated based on initial start of IMP.

These exploratory efficacy analyses will be performed using the subsequent cemiplimab monotherapy on progression set.

Objective Response Rate based on PCWG3 and iRECIST (central reading)

ORR will be analyzed separately for PCWG3 and iRECIST (central reading).

The ORR is defined as the number of patients with CR or PR as best objective response per PCWG3 (or number of patients with iCR or iPR as best objective response per iRECIST (central reading)) after start of cemiplimab treatment, divided by the number of patients in the subsequent cemiplimab monotherapy on progression set.

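### For Arm 1B patients who switch to cemiplimab, the 12-week PSA-progression confirmation rule is still timed from the first vaccine dose

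*SAP*

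**What the plan says.** SAP 8.2 fixes the date of first IMP administration. It "Is defined as first administration date/time of IMP (W_pro1 or cemiplimab), whichever was administered first". Every Arm 1B patient starts on the vaccine (W_pro1, i.e. BNT112), so that date is the first vaccine dose.

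The PSA progression (PD) rule in the same section uses that date twice. At or beyond "12 weeks after first administration of IMP. This PSA PD needs no confirmation". Below "12 weeks after first administration of IMP, this PSA PD needs to be confirmed by" a later PSA PD at 12 weeks or more, or by soft-tissue, bone or clinical progression, with no better response in between. PSA PD is one of four components of PCWG3 progression, and the earliest component sets the date. Best overall response uses assessments only up to the first progression.

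Protocol Appendix 9 contains the parent rule: "Ignore early rises (before 12 weeks) in determining PSA progression". It has no separate version for patients who switch.

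For switch patients, SAP 8.7.4.2 states that "the last measurement prior to start of cemiplimab treatment will serve as baseline measurement". It redefines target and non-target lesions and starts PFS at first cemiplimab. It counts best response, and the progression that ends PFS, DoR or PFS2, after the start of cemiplimab. It does not mention the 12-week PSA rule.

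In the Protocol 1.5 schedule PSA is drawn at every cemiplimab cycle, while "Bone scans and CT/MRI of the chest, abdomen, and pelvis will be done every 3 months".

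**The concern.** The rule exists so that a PSA rise soon after starting a treatment is not taken at face value as failure of that treatment. Switch patients start a new treatment, with a new baseline and a new PFS origin, but the period that protects against early rises was used up on the previous one. They also enter at progression, and PSA is measured every 3 weeks against imaging every 3 months. PSA is therefore likely to be the first PCWG3 component able to signal progression on cemiplimab.

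If an early reported PSA PD stands unconfirmed, PFS and PFS2 end there, and a later radiographic response cannot enter best response. The patient then also drops out of the duration-of-response analysis, or has a preceding PSA response cut short. The stated objective for this set is the anti-tumor activity of cemiplimab after vaccine progression, and an error of this kind can only make that activity look smaller.

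**Working it through.** The plan gives no figure to reproduce. The question is how much of the 12 weeks remains when cemiplimab starts.

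**Inputs**
- First scan: C3D15 (Protocol 8.1.1.1), 2 × 21 + 14 = 56 days = week 8, window ±7 days.
- Confirmation scan: 4 to 8 weeks later for soft tissue, at least 6 weeks later for bone (Protocol Appendix 9).
- Switch: within 28 days of confirmed progression (Protocol 1.3, footnote). The visit-window row of Protocol 1.5 says within 28 days of progression, so a switch on unconfirmed progression is not clearly excluded.
- Cemiplimab cycle: 3 weeks, PSA at each (Protocol 1.5).

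**Formulas.** Let T be the weeks from first vaccine dose to first cemiplimab dose. Period left on cemiplimab = max(0, 12 − T). The CemC2 draw falls at week T + 3 and the CemC3 draw at T + 6. The documents do not give T, so a range is shown for progression at the first scan.

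| Route to switch | T (weeks) | Weeks left | CemC2 at week | Must a PSA PD at CemC2 be confirmed? |
|---|---|---|---|---|
| Soft tissue, shortest | 8 + 4 + 0 = 12 | 0 | 15 | No |
| Soft tissue, longest | 8 + 8 + 4 = 20 | 0 | 23 | No |
| Soft tissue, scan 7 days early, shortest | 7 + 4 + 0 = 11 | 1 | 14 | No |
| Bone, shortest | 8 + 6 + 0 = 14 | 0 | 17 | No |
| Unconfirmed, immediate, scan 7 days early | 7 | 5 | 10 | Yes (CemC3, week 13: no) |
| Unconfirmed, immediate, scan on time | 8 | 4 | 11 | Yes (CemC3, week 14: no) |
| Unconfirmed, immediate, scan 7 days late | 9 | 3 | 12 | No |

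Progression at a later scan gives a larger T and leaves nothing. If the rule ran from first cemiplimab, every switch patient would have 12 weeks, and the first scheduled draw exempt from confirmation would be CemC5 (4 × 3 = 12 weeks).

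**Who is affected.** Compare the two clocks for a PSA PD reported at CemC2.
- PSA rises with no decline: Protocol Appendix 9 backdates progression to the first qualifying rise, so the PD date is the same under either clock.
- The rise reverses, or stable disease or response follows: timed from cemiplimab, the early PD would not be confirmed and would not count. Timed from the vaccine, it counts. For such a patient the SAP formula puts cemiplimab PFS at (21 + 1)/30.4375 = 0.72 months, well before the first 3-month scan.

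The documents give no PSA trajectories or response rates on cemiplimab, so the share of patients in the second group, and hence the effect on ORR or median PFS, cannot be computed.

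**The case against.** Four objections carry weight.

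**Section 8.7.4.2 already moves the response window.** The general best-response rule in 8.2 reads "Only assessments after first administration of IMP and prior to or at the start date of the first subsequent anti-cancer therapy will be considered" and stops at the first progression. A reader might infer that the progression on vaccine closes the window, so that no cemiplimab response could count and ORR in this set would be zero. The documents do not support that. Section 8.7.4.2 counts best response after the start of cemiplimab, and dates PFS, DoR and PFS2 by the first progression after it. The specific section governs. All that remains is that 8.7.4.2 does not say in words that the 8.2 truncation is read the same way.

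**Not every early rise becomes progression.** The SAP states: "PSA response definition based on PCWG3 will be derived based on the PSA response data reported by the investigator". Protocol Appendix 9 asks for at least 25% and at least 2 ng/mL, confirmed 3 weeks or more later. An investigator might also run the 12 weeks from cemiplimab when reporting. This stands, and it limits how often the problem arises. It does not remove it. A rise at CemC2 confirmed at CemC3 is still within 6 weeks of starting cemiplimab and is dated to CemC2. Without a stated start date, sites may also use different clocks.

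**Assumed doubling times do not measure the error.** One could calculate how fast PSA must double to reach 25% by each cycle and present the resulting short PFS as the bias. A constant doubling time is a rise with no decline, which is the pattern whose PD date backdating leaves unchanged.

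**The reach is small.** The endpoints are exploratory and untested, in a self-selected part of one arm. SAP 8.1 keeps post-switch data out of the other efficacy analyses, including the primary ORR. The iRECIST endpoints rest on central image reading and do not use PSA. A reader might also infer a biased contrast with Arm 1A, where both drugs start together, but no comparison of the switch set with Arm 1A is planned.

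**Conclusion.** The point holds, and it is minor. For the switch set the SAP resets every relevant anchor except the PSA-progression clock. When cemiplimab starts at week 12 or later, which the schedule makes usual after confirmed progression, no early-rise period remains. At the earliest window edge (week 11), 1 week remains. Switches at weeks 7 to 9, on unconfirmed or clinical progression, keep 5 to 3 weeks.

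The consequence is limited to PCWG3 best response, ORR, DoR, PFS and PFS2 in the Cemi Mono on PD set, and within it to patients with a reported early PSA PD that reverses or is followed by stable disease or response. For them the error runs toward less apparent activity. Its overall size is unknown.

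Two assumptions carry this: that PCWG3 progression in 8.7.4.2 is derived by the 8.2 rules, the only PCWG3 derivation in the SAP, and that the protocol's backdating is applied to PSA that rises without decline.

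**What to change.** Add one paragraph to SAP 8.7.4.2. For the Cemi Mono on PD set, time the 12-week PSA PD rule of 8.2 from first administration of cemiplimab, and take PSA change from Cemiplimab Baseline. As a clarification, state that the first progression in the 8.2 best-response truncation means the first after the start of cemiplimab.

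Record the change in SAP Appendix 1. Because the trial is open-label and the interim analysis has been done, show the current derivation as a sensitivity analysis.

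The cost is one paragraph and one anchor date in the programming. No new data are needed. PFS and PFS2 in the switch set may lengthen slightly relative to the current clock, and the sensitivity analysis would show by how much.

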#### 2. MEASURES OF RESPONSE:

The PCWG3 criteria for disease response in a patient are considered met if 1 or more of the following conditions occur:

- a) PSA response:
- PR: \ge 50\% decline in PSA from baseline confirmed at least 4 weeks later
- SD: Serial PSA measurements that do not meet the criteria for PR or PD
- b) Radiological response:
- Soft tissue/visceral disease:
  - CR: Disappearance of all target lesions. A reduction in short axis to <10 mm must be seen in any pathological lymph nodes. No new lesions.
  - PR: 30% decrease in the sum of the longest diameter of target lesions.
  - SD: No evidence of PD, CR or PR.
- Bone disease response
  - Bone scan is not used as part of the response criteria. Bone scans will be evaluated for progression only.
- c) Circulating tumor cell (CTC) response:
- Conversion of CTC  $\geq 5/7.5$  mL to  $\leq 5/7.5$  mL at 9 weeks. If there is a CTC response, this must be confirmed by an additional  $\leq 5/7.5$  mL result at least 4 weeks later.

CONFIDENTIAL Page 114 of 122

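### For the primary ORR, SAP 8.2 lets a PSA partial response be confirmed from 20 days where protocol Appendix 9 requires at least 4 weeks, and SAP 13.1 does not list the change

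*SAP*

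**What the plan says.** Protocol Section 8.1.1.2 refers to Appendix 9 (Section 10.9) for the response criteria. There a PSA PR is a fall of at least half: "decline in PSA from baseline confirmed at least 4 weeks later".

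SAP Section 8.2 has its own rule. A PSA PR may be confirmed by a later PSA PR, or by a later soft-tissue PR or CR, with this timing: "Which occurs within ≥ 20 days and" no later than the start of the first subsequent anti-cancer therapy. The confirming response must follow immediately on the initial one, and no worse response may lie between them. Worse responses include soft-tissue stable disease (SD) and PSA SD.

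This feeds the primary endpoint: "Overall Response of CR, PR, SD per PCWG3 is based on radiological soft tissue response or confirmed PSA response". SAP Section 8.7.1.1 uses that best response for the ORR in Part 2 Arms 1A and 1B. The source is given as "Confirmed PSA response reported by the investigator".

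SAP Section 13.1 declares two changes only: the per-protocol set with its supporting analyses, and the set for cemiplimab monotherapy on progression. The version history mentions, for PSA, only a new analysis set and added early draws.

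On PSA progression (PD), Appendix 9 says "This rise must be confirmed by a second measurement ≥3 weeks later". On dating, Appendix 9 goes back to the initial value: "the date of progression is denoted as the first measurement to meet these criteria". For a PSA PD at 12 weeks or later, SAP 8.2 says "This PSA PD needs no confirmation".

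**The concern.** The confirmation interval decides which PSA declines count as responses in the primary efficacy endpoint. With a draw every 3 weeks, moving the minimum from 28 to 20 days changes how many later values a patient must hold the decline for. The reported ORR and its confidence interval would then not be those of the protocol's criterion, and SAP 13.1 would not alert the reader.

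The PD wording raises a second, lesser question. If a single rise counts as progression, it closes the period in which a best response is sought and sets exploratory PFS and DoR dates.

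**Working it through.** **Inputs.** Cycle length is 21 days. PSA is drawn weekly in Cycles 1 and 2, then on Day 1 of each cycle. Visit windows are ±1 day for these visits to C8D1 and ±3 days from C9 (protocol Section 1.3). Study day = (cycle − 1) × 21 + day.

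**Gaps between consecutive Day-1 draws.** C3 to C8: 21 ± (1 + 1) = 19 to 23 days. C8 to C9: 21 ± (1 + 3) = 17 to 25. From C9: 21 ± (3 + 3) = 15 to 27. None reaches 28 days without a dose delay or an unscheduled draw. The draw after next lies at 42 ± 2 = 40 to 44 days, or 42 ± 4 = 38 to 46 for C7D1 to C9D1.

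**First scheduled on-treatment draw that can confirm (nominal days).**

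| PSA PR first seen (study day) | SAP, at least 20 days | Protocol, at least 28 days |
|---|---|---|
| C1D8 (8) | C2D8, 21 | C2D15, 28 |
| C1D15 (15) | C2D15, 21 | C3D1, 28 |
| C2D1 (22) | C3D1, 21 | C4D1, 42 |
| C2D8 (29) | C4D1, 35 | C4D1, 35 |
| C2D15 (36) | C4D1, 28 | C4D1, 28 |
| C3D1 to C7D1 (43 to 127) | next Day 1, 21 | Day 1 after next, 42 |

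For C1D8, C1D15 and C2D1 the SAP column holds only if the immediate-succession wording allows weekly draws in between; the SAP does not say.

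**The SAP rule that works the other way.** Soft-tissue SD between the two PSA values blocks confirmation; Appendix 9 has no such bar. Scans are due at C3D15 (day 57, window 50 to 64), C6D1 (day 106, window 99 to 113) and C8D15 (day 162). The C3D15 scan lies between C3D1 (day 43) and C4D1 (day 64). The C6D1 scan can fall in C5D1–C6D1 or C6D1–C7D1. A patient with SD on such a scan is not confirmed at the next draw, even if the PSA decline holds.

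Lengthening the interval without removing this bar would make it act more often. On nominal days, one of the six 21-day intervals starting at C2D1 and C3D1 to C7D1 has a scan strictly inside it (C3D1–C4D1). Of the corresponding 42-day intervals, four do: C2D1–C4D1, C3D1–C5D1, C5D1–C7D1 and C7D1–C9D1.

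**Size of one reclassified patient.** The final mITT number per arm is not given; I assume 19 (a count named in SAP 8.7.6) to 33 (the planned total). 100/19 = 5.3 points; 100/33 = 3.0 points. Clopper-Pearson 95% limits are the 0.025 quantile of Beta(x, n − x + 1) and the 0.975 quantile of Beta(x + 1, n − x):

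| n | 1 responder | 2 responders |
|---|---|---|
| 19 | 0.1 to 26.0% | 1.3 to 33.1% |
| 33 | 0.1 to 15.8% | 0.7 to 20.2% |

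This is the size of one reclassification, not an expected effect.

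**PSA PD, only if the entry is a single value.** Twelve weeks is 84 days after first dose, study day 85. C6D1, C7D1 and C8D1 are safely past it; C5D1 is past it only if not drawn early. PFS months = study day / 30.4375: 106, 127 and 148 give 3.5, 4.2 and 4.9 months, against 162/30.4375 = 5.3 for progression first shown at the C8D15 scan. A rise that is later confirmed keeps the same date under both rules, so only unconfirmed rises differ.

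**The case against.** **The SAP may add detail.** Protocol Section 9.4 says the SAP will be more technical. But 20 days in place of 28 is a different threshold, and no reason is given. Fitting the rule to a 21-day cycle may be sensible; it would still need to be declared.

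**A later confirming draw is a delay, not a different answer.** This stands in part. A patient who holds the decline to the 42-day draw is a responder under both rules. The result differs only if the decline is lost by then or no later draw exists. EoT and safety follow-up draws can supply a late value for some who stop treatment.

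**The SAP is stricter for some patients.** This stands. The intervening-SD bar removes responders whom Appendix 9 would count.

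**The investigator entry may already be confirmed.** If a PSA PR is entered only after the protocol's 4 weeks, the 20-day check is an extra check and relaxes nothing. The SAP speaks of an initial PSA PR that it then seeks to confirm, which suggests per-visit entries but does not prove it.

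**The reader can see the PSA contribution.** Radiology-only ORR (Table 14.2.1.1.4) and PSA-only ORR (Table 14.2.2.5.4) are planned, and Listing 16.2.6.2 covers PSA. The tables show how far PSA drives the composite. The PSA-only table rests on the same confirmed response, so it does not separate 20 from 28 days; the listing would allow a check by hand.

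**Conclusion.** The point holds for PSA PR: SAP 8.2 changes an Appendix 9 rule that feeds the primary ORR, and Section 13.1 does not list it. Where no worse response intervenes, a PR first seen at C2D1 or at a Day-1 draw from C3D1 to C7D1 can be confirmed one Day-1 draw earlier than the protocol allows (21 against 42 days). This rests on scheduled draws without dose delay, on per-visit investigator entries and, for C2D1, on a loose reading of immediate succession. It should be fixed; my confidence is medium, because the documents hold no PSA results.

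Three stronger readings are tempting and not supported:

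- A reader might infer that the SAP inflates the ORR. The shorter interval can add responders and the intervening-SD bar can remove them, so the net direction is unknown.
- A reader might infer that the SAP has dropped confirmation of PSA PD. Whether the entry already contains the second value is not stated. By-visit tabulation of entries (SAP 8.7.3.1) and the rule for entries before week 12, which looks for "Another PSA PD that occurred immediately after the initial PSA PD", suggest single-visit entries without settling it. This is a request for clarification.
- A reader might infer that the two-stage test is compromised. SAP 8.7.6 records that enrollment in both arms stopped after the interim analysis, so the 33-patient rule no longer drives a decision. What is affected is the reported ORR and its interval.

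**What to change.** For the primary ORR:

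1. Derive confirmed PSA PR from the numeric PSA values already in the database: a decline of at least 50%, confirmed at 28 days or more.
2. State a visit-window tolerance, because the nominal 28-day gaps in Cycles 1 and 2 can be 26 or 27 days.
3. Do not let an intervening soft-tissue SD alone cancel a PSA PR held at both draws. Without this step, the longer interval would make the SAP stricter than Appendix 9.
4. Define what it means for the confirming response to follow immediately.
5. Report the current 20-day rule as a sensitivity analysis.
6. List the difference in SAP 13.1.

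For PSA PD, state whether the investigator entry already includes the second measurement. If not, apply Appendix 9 confirmation (3 weeks or more later, dated at the first qualifying value) in BOR, PFS and DoR. Add a sensitivity analysis that counts PSA PDs with no later draw as events, and give their number, because censoring them may be informative.

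The cost is SAP wording and a reprogrammed derivation on data already collected. The downside is that PSA PRs confirmed only at 20 to 27 days leave the main ORR, apart from any that the stated tolerance admits. If PD confirmation is added, a PSA PD at a patient's last draw stays unconfirmed in the main analysis.
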